# SUMMARY OF POST GRADUATE THESIS PROTOCOL

1. Study title	: A comparative study to assess efficacy of
	Intralesional MMR (Measles, Mumps, Rubella)
	vaccine and Intralesional Vitamin D3 in treatment
	of Warts
2. Name of the author	: [name]
3. Department	: Department of Dermatology and Venereology
4. Name of co- author	: [name]
	Associate Professor
	Department of Dermatology and Venereology
5. Name of Co-author	: [name],
	Associate Professor
	Department of Dermatology and Venereology
6. Email ID of the author and	d co-authors: [contact] &
	[contact]
	[contact]
7. Rationale of the research	: As per my literature search,
	1. No previous studies on immunotherapy in wart
	have been conducted in our country
	2. No comparative studies have been done to
	compare IL MMR and IL vitamin D3 in treatment
	of wart hence we aim to establish efficacy of
	each and compare the two in our country
8. Objectives	: Primary Objectives:

- To determine the efficacy of IL MMR vaccine in the treatment of Wart
- To determine the efficacy of IL vitamin D in the treatment of wart
- To compare the efficacy of IL MMR vaccine and IL Vitamin D

### Secondary Objectives:

- To determine the frequency of patients with different types of warts visiting Dermatology outpatient department of BPKIHS
- 2. To determine the side effects of IL MMR vaccine and IL Vitamin D in treatment of wart
- To determine Dermatology life quality index (DLQI) in wart patients.

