# Secondary Objective:

- To determine the clinical and demographic profile of patients with different types of warts visiting Dermatology outpatient department of BPKIHS
- 2. To determine the side effects of IL MMR vaccine and IL Vitamin D in treatment of wart
- 3. To determine Dermatology life quality index (DLQI) in wart patients.

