# MATERIALS AND METHODOLOGY

## Materials:

The study population will be all patients clinically diagnosed with warts visiting the Dermatology outpatient department of BPKIHS, Dharan.

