# Conflict of interest: None

**Sampling Technique:** Census method with all consecutive patients meeting inclusion criteria for initial 6 months

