### **Inclusion criteria**

- 1. Clinically diagnosed patients who have more than three warts or single wart in difficult to treat sites (periungual, palms and soles)
- 2. Age >/= 12 years

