### **Exclusion criteria**

- 1. Patients under any systemic or topical treatment of warts for the last 4 weeks
- 2. Patients with a past history of an allergic response to MMR or any other vaccine or Vitamin D
- 3. Patients with current acute febrile illness or any bacterial infection
- 4. Immunosuppressed patients
- 5. Pregnant or lactating women
- 6. Patients having a past history of asthma, allergic skin disorders or convulsions
- 7. Patients with keloidal tendency
- 8. Patient refusal for consent
- 9. Treating physician's decision to give other modality of treatment
- 10. Patients with hypervitaminosis D, muscle weakness, bone pain, altered sensorium

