### Methodology

Based on the computer generated random number table, patients will be assigned to either Group A or Group B once they come to OPD. Informed consent will be taken. After that detailed information of all the patients satisfying inclusion criteria will be recorded in preset pro forma. This will include personal data, past history, medical history, drug history, clinical data like site, size, number, distribution of lesions. History of muscle weakness, bone pain, altered sensorium, anaphylaxis and immunosuppression will also be taken. In patients of group B serum vitamin D level will be measured after 20 days of 3rd dose and 1 month after the last dose to ensure safe monitoring. Photographs of the lesions will be taken before the first treatment session, in every treatment session and 3 months after last session.

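### The first secondary objective asks about the clinic's wart patients, but the data planned describe only patients eligible by wart number, site and age

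*Combined protocol and SAP*

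**What the plan says.** The objective appears in two forms. The summary, under Secondary Objectives, has "To determine the frequency of patients with different types of warts visiting Dermatology outpatient department of BPKIHS". The main text, under Secondary Objective, has "To determine the clinical and demographic profile of patients with different types of warts visiting Dermatology outpatient department of BPKIHS". Both refer to people attending the department. The Materials paragraph names the target group: "The study population will be all patients clinically diagnosed with warts visiting the Dermatology outpatient department of BPKIHS, Dharan".

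The data come from a narrower group:

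- Sampling Technique: "Census method with all consecutive patients meeting inclusion criteria for initial 6 months".
- Inclusion criteria: patients with "more than three warts or single wart in difficult to treat sites (periungual, palms and soles", plus an age limit (12 or over in the main text, over 12 in the summary).
- Methodology: after allocation and consent, "detailed information of all the patients satisfying inclusion criteria will be recorded in preset pro forma".

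No log of ineligible wart patients, register of wart attenders or count of total attendance is described. The Statistical analysis section offers only general descriptive statistics and names no denominator for this objective.

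**The concern.** A frequency or profile needs a defined population and a sample that represents it. Here the population is the clinic's wart patients, while the sample is filtered on number of lesions, site and age before anything is recorded. Number and site are part of what distinguishes one wart type from another, and age is part of the demographic profile. The filter is therefore tied to the quantities to be estimated. More patients would not help, because those outside the criteria have no chance of being counted.

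At stake is one of three secondary objectives. Reported under its present wording, the table of wart types and patient characteristics would be read as a description of the department's wart patients, which the plan does not support.

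**Working it through.** The plan gives no figure for this objective. Its sample-size calculation (18.54 per group, raised to 30) serves the efficacy comparison only. The check is therefore mainly a comparison of sections.

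**Step 1: who can be counted.** Reading the inclusion criteria literally, for patients who meet the age limit:

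| Number of warts | Periungual, palmar or plantar | Other sites |
|---|---|---|
| 1 | eligible | not eligible |
| 2 or 3 | not eligible | not eligible |
| more than 3 | eligible | eligible |

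Patients below the age limit are not eligible in any cell.

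**Step 2: is the filter related to type?** The Classification of warts section says that it is:

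- Mosaic warts are usually plantar and multiple.
- Endophytic common warts are typically palmar or plantar, and the deep plantar ones are most often multiple.
- Myrmecia are palmar or plantar and more often single.
- Papillomatous warts are found mostly on the face, head, neck and folds.

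A single myrmecia on the sole enters. A single papillomatous wart on the face does not. A patient with two or three deep plantar warts does not enter either.

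**Step 3: is the filter related to the demographic profile?** The Review of Literature puts the highest prevalence in school-aged children. The age limit removes the younger part of that group, so the enrolled age profile is cut off from below.

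**Step 4: can the bias by type be sized?** Let t be the true share of periungual, palmar and plantar disease among the clinic's wart patients. Let e1 and e2 be the probabilities of eligibility at those sites and elsewhere. The share in the sample is

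t·e1 / (t·e1 + (1 − t)·e2).

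The documents give none of these three values. With an **assumed** t of 0.30 and **assumed** eligibility pairs:

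| e1 | e2 | Calculation | Share in sample |
|---|---|---|---|
| 0.9 | 0.3 | 0.27 / (0.27 + 0.21) | 56.3% |
| 0.7 | 0.5 | 0.21 / (0.21 + 0.35) | 37.5% |
| 0.5 | 0.7 | 0.15 / (0.15 + 0.49) | 23.4% |
| 0.3 | 0.9 | 0.09 / (0.09 + 0.63) | 12.5% |

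If e1 = e2 the sample share is 30% and there is no bias. From Step 1, e1 is the chance of having exactly one wart or more than three, among patients with warts at the difficult sites. e2 is the chance of having more than three elsewhere. Which is larger depends on how lesion counts are distributed at each kind of site, and the documents do not say.

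**Step 5: sampling error, for scale.** For an assumed share of 30% in 60 patients, the 95% half-width is 1.96 × √(0.30 × 0.70 / 60) = 0.116, or 11.6 percentage points. Selection bias comes on top of this and does not shrink with sample size.

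**The case against.** The best reply is that neither form of the objective says it covers every attender. The main-text form, a clinical and demographic profile, can be read as an ordinary baseline description of recruited patients. On that reading nothing is wrong except the wording. This has force for the main text. It fits the summary's word for frequency poorly, and the Materials paragraph, which takes all wart patients visiting the department as the study population, points the other way. If enrolled patients are meant, a wording change settles the matter.

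Three stronger readings are tempting and should not be adopted:

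- *Palmar and plantar types will be over-counted.* A reader might infer this because a single wart at those sites qualifies. But the literal criterion also drops two or three warts at the same sites, and the classification calls some palmoplantar types multiple. The direction is not established.
- *Immunosuppressed patients, and those covered by "Treating physician's decision to give other modality of treatment", are certainly missing from the data.* These are exclusion criteria, whereas Methodology ties recording to the inclusion criteria. The proforma has fields for HIV, pregnancy and immunosuppressive drugs. Whether patients who meet the inclusion criteria but are then excluded stay on record is left open.
- *The objective will be answered wrongly.* A table labelled as the profile of enrolled patients would be correct. The error lies in extending it to the clinic.

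It is also fair to say that this is a descriptive secondary objective with no test or sample size attached.

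**Conclusion.** The concern holds in a limited form. As planned, the data can describe enrolled patients. They cannot give the frequency of wart types, or the clinical and demographic profile, for wart patients attending the department. This rests on the text alone: the target in the objectives and Materials, the filter in Sampling Technique, Inclusion criteria and Methodology, and the link between type, site and number in the classification.

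The size and direction of the bias by type cannot be stated. The 12.5% to 56.3% range reflects assumed inputs and shows only that the effect could be material in either direction. The bias would vanish if eligibility were unrelated to type, which the classification makes implausible. The efficacy objectives, the allocation and the treatment comparison are unaffected, so this is a minor point.

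**What to change.** Choose one of two courses and use a single wording in the summary and the main text.

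1. **Narrow the objective.** For example: *to describe the clinical and demographic profile, including wart type, of patients enrolled in the trial*. Limit the conclusion in the same way. The cost is a wording change and a narrower claim.
2. **Keep the clinic-level objective and collect what it needs.** For every wart patient seen in the six-month recruitment window, record one anonymous line: wart type, site, number of warts, age, sex, and eligible or the reason not. Use this tally as the denominator. If frequency among all dermatology attenders is meant, also record total attendance. The tally should start with recruitment, since patients not recorded then are hard to recover. It should be covered by the ethics approval, because Methodology places consent before recording. The cost is a little extra recording; consecutive recruitment already implies checking each wart patient for eligibility.

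Under either course, state whether patients who meet the inclusion criteria but are then excluded are kept in the descriptive data.

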### 9. Research Hypothesis : Null Hypotheses (H0):

IL MMR vaccine is not better than IL Vitamin D in

the treatment of wart

### Alternative hypothesis:

IL MMR vaccine is better than IL Vitamin D in the treatment of wart

### 10. Material & Methods:

- (a) Whether study involves Human/animals or both : Human only
- (b) Population/ participants : Patients with warts visiting Dermatology outpatient

department

(c) Type of study design : Prospective comparative longitudinal Study

(d) Setting : Outpatient Department of Dermatology and Venereology, BPKIHS

# (e) Sample Selection criteria:

# (i) Inclusion Criteria

- Clinically diagnosed patients who have more than three warts or single wart in difficult to treat sites (periungual, palms and soles)
- 2. Age > 12 years

÷

#### (h) Probable duration of study : one year

(i) Parameter/Variables to be measured: Age, sex, race, occupation, number of

warts, site of warts, response rate,

DLQI

- (j) Outcome measures : Response rate of warts to IL MMR and IL Vitamin D3
- (k) Statistical methods to be employed :
- a. **Data handling:** Data were entered in Microsoft Excel 2010 (Microsoft Corporation, Redmond, Washington, USA) and statistical analysis was done using Statistical Package for the Social Sciences 10.5 version (Chicago, Inc)
- b. Coding: Alpha numerical code was used
- c. **Monitoring:** Data was entered after every day of work and supervised by guide.
- d. Statistical analysis: will be conducted as per both per-protocol and intentionto treat population (defined as all enrolled patients to whom study drug will be given; with the last observation carried forward) basis using two sided tests.
  For *descriptive statistics*, percentage, mean, S.D., median, and minimum, maximum will be calculated along with graphical and tabular presentation.
  For *inferential statistics*, statistical methods that will be used are as follow
- Chi square test and Fisher's exact test to compare the categorical data between the groups.
- Paired t test for comparing normally distributed continuous variables (pretreatment and post treatment DLQI) at different time point within the groups.
- 3. Mann- Whitney U test to compare the not normally distributed variables (age,

duration of illness, size, number)

4. Kaplan–Meier curves to compare the response rate (complete, excellent, good or poor response) on each follow up visit (week 3, 6, 9, 12) between the groups.

Test of significance will be considered when value of  $p \le 0.05$ .

- (I) Ethical clearance : Will be obtained from the Institutional Review
   Committee (IRC), BPKIHS and Nepal Health
   Research Council (NHRC)
- (m) Permission to use copyright questionnaire/Proforma : N/A
- **11. For Intervention trial**
- a. Permission from Drug Controller of Nepal: not required
- b. Safety measure :will be applied
- c. Plan to withdraw : As per the decision of treating physician
- 12. Maintain the confidentiality of subject : Yes
- 13. References : attached
- 14. Whether available resources are adequate: adequate
- **15. Other resources needed** : not needed
- 16. Cost involved (Approx in NRS)
- a. Investigations :60,000 (approximate)
- b. Surgery :NA
- c. Drugs :64,500 (approximate)

Group A- MMR cost × number of participants × number of sessions per patient

=350×30×5

=52,500

Group B- Vitamin D cost  $\times$  number of participants  $\times$  number of sessions per patient

=80×30×5

=12,000

Total cost = 64,500

Both MMR and Vitamin D are easily available in local pharmacy.

# 17. Who will bear the cost of the requirements? Patient

## 18. ANNEXURE:

a. Participants record form (clinical data sheet): Attached

## b. Participant Information sheet

i. Attached English

# c. Participant Informed consent form

i. Attached English

# ABBREVIATIONS

ANOVA	-	Analysis of Variance
BCG	-	Bacillus Calmette Guerin
BPKIHS	-	BP Koirala Institute of Health Sciences
DLQI	-	Dermatology Life Quality Index
DNA	-	Deoxyribonucleic Acid
DNCB	-	Dinitrochlorobenzene
DPCP	-	Diphenylcyclopropenone
G	-	Gauze
HPV	-	Human Papilloma Virus
IOE	-	Institute of Medicine
IFN	-	Interferon
IL	-	Intralesional, Interleukin
IRC	-	Institutional Review Committee
MD	-	Doctor of Medicine
MMR	-	Measles, Mumps, Rubella
NA	-	Not applicable
NHRC	-	Nepal Health Research Council
NK	-	Natural Killer
OPD	-	Outpatient Department
QoL	-	Quality of Life
RCT	-	Random Control Trial
SADBE	-	Squaric acid dibutyl ester
TEIB	-	Triethyleneiminobenoquinone
Th	-	T- helper
TLR	-	Toll like receptor
VAS	-	Visual Analogue scale
VDR	-	Vitamin D receptor
VDRA	-	Vitamin D receptor activator

## INTRODUCTION

Warts are papulonodular epidermal lesions with a horny or papillomatous surface caused due to infection by human papillomavirus (HPV).

Cutaneous warts occur in 7% to 10% of the general population, with a maximum incidence between the ages of 12 and 16 years. Warts can persist as it is for years and then spontaneously clear at any time from a few months to a few years. In children, clearance can occur even after only a few months, with 50% at 1 year and about 65%–78% by 2 years.  The rate of clearance is influenced by factors like virus strain, host immune status, extent, and duration of warts 

HPVs are ubiquitous, epitheliotropic non-enveloped small double-stranded DNA viruses. Over 150 types of papillomavirus have been identified based on DNA studies and serological detection of type-specific antibodies against HPV capsid antigens. Among them verruca vulgaris or common warts are usually caused by Human Papilloma Virus (HPV) types 1, 2, 4, 27 or 57, and plane warts by HPV types 3 or 10.

The transmission of warts occurs from direct contact or indirectly via fomites. Usually, warts spread in swimming pools and bathrooms as the skin is macerated and is more prone to minor abrasions and infections thus serving as conduits for HPV to the basal keratinocytes, the primary targets for HPV infection.  There they undergo a latent phase of slow replication and then induce epidermal hyperplasia and hyperkeratosis as the epidermis grows superficially. 

The destructive therapies in treatment of wart include salicylic acid, trichloroacetic acid, cryotherapy, silver nitrate, phenol, cantharidin, surgical interventions and lasers; antiproliferative agents include bleomycin, vitamin D analogs, podophyllin, podophyllotoxin, and 5-fluorouracil; antiviral agents include cidofovir and retinoids. Other modalities include hypnotherapy, acupuncture, local hyperthermia, therapeutic vaccination, and combinations of the previous agents.

Destructive therapies are usually uncomfortable, require multiple sessions and individual treatment of each wart, and are often associated with variable efficacy, high recurrence, and significant adverse effects such as scarring. Hence immunotherapy is becoming more and more popular, especially in the treatment of refractory cutaneous and genital warts. These include various topical, intralesional (IL), and systemic agents.

Immunotherapy is defined as a type of biological therapy that uses substances to stimulate or suppress the immune system to help the body fight cancer, infection, and other diseases. Immunotherapy can affect the immune system in general or can be cell-specific. 

Immunotherapeutic agents include:

- 1. Prophylactic vaccination using viral antigens
- 2. Therapeutic vaccination using viral antigens
- 3. Pro-inflammatory cytokines and tumor destroyers (interferon)
- 4. Immune enhancement
  - a. Topical (imiquimod)
  - b. Systemic (cimetidine, levamisole, zinc sulfate)

- 5. Induction of delayed (cellular) hypersensitivity
  - a. Intradermal (tuberculin, candidin, trichophyton, mumps antigen, BCG,
     Vitamin D)
  - b. Topical (DNCB, DPCP, SADBE, TEIB)
- 6. Combination treatment 

The exact mechanism of immunotherapy is not yet known but it is believed that the injection to the HPV-infected tissue induces a strong nonspecific proinflammatory signal and attracts the antigen-presenting cells. This is associated with the release of cytokines such as IL-2, IL-8, IL-12, IL-18, tumor necrosis factor–  $\alpha$ , and interferon- $\gamma$ . This then promotes a Th1 cytokine response which leads to the activation of cytotoxic T cells and natural killer cells i.e. delayed-type hypersensitivity reaction leading to the eradication of the HPV-infected cells. Furthermore, the trauma of the injection may also cause a resolution in previously sensitized individuals. Since intralesional antigen immunotherapy enhances recognition of the virus by the immune system it causes clearance of both treated and untreated lesions and helps to prevent future clinical infection through induction of long-term acquired immunity to HPV.

Measles, Mumps Rubella (MMR) vaccine is included in immunization schedule so pre-sensitization skin test is not needed as all patients are expected to be immune. In 1989, monovalent measles vaccine was introduced in Nepal for vaccination of infants at age nine months. In 2013, measles-rubella (MR) vaccine was introduced into the national routine immunization schedule and replaced monovalent measles vaccine. The presence of three different antigens in MMR

increases the sensitivity to the injected antigen and decreases the likelihood of anergy. Side effects of MMR include pain during injection, flu-like symptoms, pruritus and burning sensation.

Intralesional (IL) vitamin D is a novel addition to therapies in warts as it is a simple, effective, well-tolerable, and inexpensive method with negligible local and systemic side effects

Side effects of Vitamin D3 include transient mild to moderate pain, edema at the site of injection, resolving within 1 week mild erythema. Further it would be safer to measure serum vitamin D and calcium levels before and after intralesional vitamin D treatment to prevent possible hypervitaminosis D.

Vitamin D3 acts on the principle of immunotherapy by stimulating cell-mediated immunity In addition, it is also claimed to regulate epidermal cell differentiation and proliferation and may modulate cytokine production through its action upon vitamin D receptors(VDRs). VDRs are present in the keratinocytes, melanocytes, fibroblasts, and immune system cells of the skin. Activation of Toll-like receptor (TLR) of human macrophages up-regulates the expression of vitamin D receptor and vitamin D1- hydroxylase genes, leading to induction of the antimicrobial peptide like thymic stromal, lymphopoietin and cathelecidin.  It also reduces the synthesis of IL1a and IL6 resulting in decreased inflammation. VDR activators (VDRAs) have been shown to inhibit cell replication and have immunomodulatory properties.

It is supposed that combining intralesional immunotherapy with a destructive treatment method might enhance the efficacy, shorten the treatment duration, and reduce the possible side effects.

# **RATIONALE OF THE STUDY**

Intralesional Immunotherapy is a emerging method of treatment of wart in which injection in a single wart causes the resolution of distant warts as well. Compared to other destructive modalities, it is more effective and comfortable for the patient as it obviates the need for individual treatment of each wart. In addition it has a lower rate of recurrence, avoids adverse effects such as scarring, is more cost-effective in multiple warts and decreases the time a physician has to spend on each patient. Further both injection MMR and Vitamin D3 are readily available as compared to other immunotherapeutic agents like PPD and candida antigen.

IL MMR vaccine has been used for a longer time than IL vitamin D and there are more comparative studies showing efficacy of MMR vaccine with rates of clearance ranging from 70.4% to 82.4%. The clearance rates for IL vitamin D ranges from 40% to 90%. As per Committee to Review Adverse Effects of Vaccines; Institute of Medicine (IOE), there is evidence of causal relationship between MMR vaccine and measles inclusion body encephalitis in individuals with demonstrated immunodeficiencies. Hence immunodeficiency is one the exclusion criterias for MMR administration.

The advantages of vitamin D over MMR vaccine are cost-effectiveness, nonrequirement of maintenance of cold chain, easy availability, and feasibility of use in immunosuppressed patients.

As per Institute of Medicine (IOM), the tolerable upper intake of vitamin D is 4000 IU/day for anyone older than 9 years such that annual maximum dose will be 1,460,000 IU. The total amount of vitamin D that we will be administering will be

1,500,000 IU. Furthermore, since we are giving it intralesionally systemic absorption is likely to be low although data on exact amount of IL vitamin D that gets absorbed systemically is not available. In other studies, patients have been evaluated clinically for signs and symptoms of hypervitaminosis D however, no signs of toxicity were observed. 

As per my literature search,

- 1. No previous studies on immunotherapy in wart have been conducted in our country
- No comparative studies have been done to compare IL MMR and IL vitamin D3 in treatment of wart hence we aim to establish efficacy of each and compare the two.

